6.5.4 Stopping Rules

The DSMB will determine whether to stop the study for early evidence of intervention safety problems after a thorough review of interim data. Interim reports will provide cumulative enrollment figures and cumulative adverse birth outcomes, serious adverse events (classified according to grade), sorted by study arm. Brief clinical descriptions of key events will also be provided. The PI will be responsible for immediately reporting to the funding agency any temporary or permanent suspension of the project and the reason for the suspension.

6.5.5 Adjustment of Confidence Intervals and p–values

As appropriate we will adjust p–values and confidence intervals taking into account the specified error spending functions and interim evaluation of the data.

6.5.6 Interim Analysis for Sample Size Adjustment

The sample size will not be adjusted based on the results of the interim analysis.

6.5.7 Practical Measures to Minimize Bias

The study will establish and control who will have access to what information at each stage of the trial. Uncontrolled reporting of interim analyses to study investigators responsible for recruiting subjects will not occur.

The following measure will be taken to minimize bias:

- Only the study statistician and assistant statistician will perform the interim analysis.
- Only the statisticians and the DSMB will see any data or analyses at the interim analysis
- No information will be publically available following an interim analysis
- Information will be provided to the sponsor and investigators as per recommendation of the study DSMB.
- Only the statisticians will be unblinded at for the interim analysis

6.5.8 Documentation of Interim Analyses

Snapshots of the data available at each interim analysis will be preserved, as will all documentation of analysis plans, programming code and reporting provided at the interim analysis.

6.6 Multi–center Studies

(ICH E3;9.7.1, 11.4.2.4. ICH E9; 3.2)

This is a single center study.

6.7 Multiple Testing

(ICH E3; 9.7.1, 11.4.2.5. ICH E9; 2.2.5)

This study has one primary endpoint. The preservation of the overall significance level is of importance and as there are more than two treatment groups, secondary analyses comparing multiple groups may require adjustment of p–values and confidence intervals.

7 Summary of Study Data

All continuous variables will be summarized using the following descriptive statistics: n (non–missing sample size), mean, standard deviation, median, maximum and minimum. The frequency and percentages (based on the non–missing sample size) of observed levels will be reported for all categorical measures. All summary tables will be structured with a column for each treatment and will be annotated with the total population size relevant to that table/treatment, including any missing observations.

7.1 Trial Profile

The overall study profile will be presented as a figure following CONSORT guidelines. The total numbers of women screened, excluded during screening (including criteria for exclusion) and enrolled will be presented. The numbers of women enrolled in each treatment arm and followed through each stage of the trial profile are presented in skeleton Table 7 below.

Table 7. Trial profile

	Treatment arm		
	3 dose SP	3 dose DP	Monthly DP
Enrolled and randomized	###	###	###
Withdrawn before 1 st dose of study drugs*	###	###	###
Received at least 1 dose of study drugs	###	###	###
Withdrawn before delivery*	###	###	###
Delivered	###	###	###
Withdrawn after delivery*	###	###	###
Completed 6 week post-partum visit	###	###	###

* Specific reasons for premature study withdrawal will be reported

7.2 Baseline Characteristics

Skeleton table of all baseline variables collected on the day of enrollment that will be presented are provided in Table 8 below.

Table 8. Baseline characteristics of study participants randomized to IPTp

Characteristic	Treatment arm		
	3 dose SP (n=XXX)	3 dose DP (n=XXX)	Monthly DP (n=XXX)
Age in years, mean (SD)			
Gestational age in weeks, mean (SD)			
Gestational age categories, n (%)			
12–16 weeks			
>16–20 weeks			
Previous pregnancies, n (%)			
0			
1			
≥ 2			
Bednet ownership, n (%)			
None			
Untreated net			
ITN			
Household wealth index, n (%)			
Lowest tertile			
Middle tertile			
Highest tertile			
Weight in kg, mean (SD)			
Height in cm, mean (SD)			
Laboratory values, mean (SD)			
WBC count per mm ³			
Neutrophil count per mm ³			
Platelet count per mm ³			
Hemoglobin g/dL			
ALT IU/L			
Detection of malaria parasites by LAMP, n (%)			

7.3 Treatment Adherence

During pregnancy, women will be given 1 of 3 treatment regimens: 1) SP given 3 times during pregnancy, 2) DP given 3 times during pregnancy, or 3) DP given every

Statistical Analysis Plan PROMOTE–II Birth Cohort 1 – Pregnant women

4 weeks during pregnancy. Each treatment with SP will be given as a single dose consisting of 3 full strength tablets. Each treatment with DP will consist of 3 full strength tablets given once a day for 3 consecutive days. In addition, placebos will be used to mimic the identical dosing strategy such that every 4 weeks women will receive two drugs on day 1 (SP and placebo, DP and placebo, or two placebos) followed by one drug on days 2 and 3 (DP or placebo). Two placebos will be used, one that mimics the appearance of SP and one that mimics the appearance of DP. Administration of all study drugs will be double blinded. All doses of study drugs will be pre-packaged by a study pharmacist and administered by a study nurse blinded to the study participant’s treatment regimen. All doses of SP (or SP placebo) administered will be directly observed in the clinic. For DP (or DP placebo), the first of the 3 daily doses will be directly observed in the clinic and the 2nd and 3rd daily doses will be administered at home using pre-packaged study drugs in opaque envelopes with dosing instructions written on the outside. For doses of study drugs administered in the clinic, if a study participant vomits the study drug within 30 minutes of administration, the drug will be re-administered. For doses of study drugs administered at home, if a study participant vomits the study drug within 30 minutes of administration or study drug is lost, the study participant will be instructed to come to the study clinic as soon as possible where the study drug will be re-administered/replaced. Measures of treatment adherence are summarized in skeleton Table 9 below.

Table 9. Measures of treatment adherence

	Treatment arm		
	3 dose SP	3 dose DP	Monthly DP
At the level of each individual woman receiving at least one dose of study drugs			
At least one dose of study drug held for adverse event	n/N (%)	n/N (%)	n/N (%)
Missed at least 1 course of study drugs (all 3 doses)	n/N (%)	n/N (%)	n/N (%)
Reported not taking at least 1 dose of study drug at home	n/N (%)	n/N (%)	n/N (%)
At the level of each scheduled dose of study drug			
Study drugs (all 3 doses) held for adverse event	n/N (%)	n/N (%)	n/N (%)
Study drugs (all 3 doses) missed	n/N (%)	n/N (%)	n/N (%)
Reported not taking day 2 dose of study drugs at home	n/N (%)	n/N (%)	n/N (%)
Reported not taking day 3 dose of study drugs at home	n/N (%)	n/N (%)	n/N (%)

8 Efficacy Analyses

8.1 Efficacy outcomes

Definitions and criteria used to generate estimates of all primary and secondary efficacy outcomes are presented in Table 10 below. For women with non-singleton birth (i.e. twins), dichotomous delivery outcomes at the level of the individual child/placenta will be based on whether the outcome was present in either child/placenta.

Table 10. Primary and secondary outcomes

Outcome	Category	Type of measurement	Timing of measurement	Numerator	Denominator	Missing data	Imputation
Placental malaria by histopathology	Primary outcome	Proportion	At delivery	Placental tissue samples with parasites or pigment detected	Number of placentas examined	No placental tissue sample collected	None
Placental parasitemia using microscopy	Secondary outcome	Proportion	At delivery	Placental blood samples with parasites detected by microscopy	Number of placental blood samples examined	No placental blood sample collected	None
Placental parasitemia using LAMP	Secondary outcome	Proportion	At delivery	Placental blood samples with parasites detected by LAMP	Number of placental blood samples examined	No placental blood sample collected	None
Maternal parasitemia using microscopy	Secondary outcome	Proportion	At delivery	Maternal blood samples with parasites detected by microscopy	Number of maternal blood samples examined	No maternal blood sample collected	None
Maternal parasitemia using LAMP	Secondary outcome	Proportion	At delivery	Maternal blood samples with parasites detected by LAMP	Number of maternal blood samples examined	No maternal blood sample collected	None
Cord blood parasitemia using microscopy	Secondary outcome	Proportion	At delivery	Cord blood samples with parasites detected by microscopy	Number of cord blood samples examined	No cord blood sample collected	None
Cord blood parasitemia using LAMP	Secondary outcome	Proportion	At delivery	Cord blood samples with parasites detected by LAMP	Number of cord blood samples examined	No cord blood sample collected	None
Spontaneous abortion	Secondary outcome	Proportion	At delivery	Delivery at < 28 weeks gestational age	All deliveries	Withdrawn prior to delivery	None
Stillbirth	Secondary outcome	Proportion	At delivery	Infant born deceased	Deliveries \geq 28 weeks gestational age	Withdrawn prior to delivery or < 28 weeks gestational age	None

Statistical Analysis Plan PROMOTE-II Birth Cohort 1 – Pregnant women

Low birth weight	Secondary outcome	Proportion	At delivery	Birth weight < 2500 gm	Deliveries \geq 28 weeks gestational age	Withdrawn prior to delivery or < 28 weeks gestational age or no birth weight	Inferred if no birth weight but weight available with 7 days of birth
Preterm delivery	Secondary outcome	Proportion	At delivery	Gestational age < 37 weeks	Deliveries \geq 28 weeks gestational age	Withdrawn prior to delivery or < 28 weeks gestational age	None
Congenital malformation	Secondary outcome	Proportion	At delivery	Any congenital malformation documented on exam	Deliveries \geq 28 weeks gestational age	Withdrawn prior to delivery or < 28 weeks gestational age or infant unavailable for examination	None
Composite adverse birth outcome	Secondary outcome	Proportion	At delivery	Any of the following: spontaneous abortion, stillbirth, low birth weight, preterm delivery, or congenital malformation	All deliveries	Withdrawn prior to delivery	None
Symptomatic malaria during pregnancy	Secondary outcome	Incidence	Time at risk during pregnancy	Number of episodes of fever and positive blood smear by microscopy	Duration of observation from day following 1 st dose of study drugs to delivery or premature study withdrawal	None	None
Parasitemia during pregnancy detected by LAMP	Secondary outcome	Proportion	At the time of each routine visit	Maternal blood samples with parasites detected by LAMP	Routine visits at 20, 24, 28, 32, 36, and 40 weeks of gestational age following 1 st dose of study drugs to delivery or premature study withdrawal	Missed routine visits or samples not collected	None
Maternal anemia	Secondary outcome	Proportion	At the time of each routine visit and at delivery when phlebotomy done	Hemoglobin level < 11 g/dL	Routine visits at 20,28, 36 weeks of gestational age following 1 st dose of study drugs to delivery or premature study withdrawal	Missed routine visits or sample not collected when scheduled for phlebotomy	None

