3.2.2. Secondary Outcomes

- **Prevalence of placental parasitemia:** Proportion of placental blood samples positive for parasites by microscopy or LAMP
- **Incidence of maternal malaria:** Episodes of fever and positive blood smear by microscopy

- **Prevalence of adverse birth outcomes:** Proportions of birth outcomes that include congenital malformations, preterm delivery, late spontaneous abortion, LBW (<2500g), stillbirth, or a composite of all of these
- **Incidence of adverse events:** Adverse events stratified by type, severity score and relationship to study drugs
- **Prevalence of anemia:** Proportion of routine hemoglobin measurements < 11 g/dL & < 8 g/dL
- **Prevalence of asymptomatic parasitemia:** Proportion of routine monthly samples positive for parasites by LAMP

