4.1 General Study Design and Plan

(ICH E3;9)

This will be a double-blinded randomized controlled phase III trial of 300 HIV uninfected pregnant women and the children born to them. The study interventions will be divided into two phases. In the first phase, HIV uninfected women enrolled at 12–20 weeks gestation will be randomized in equal proportions to one of three IPTp treatment arms: 1) 3 doses of SP, 2) 3 doses of DP, or 3) monthly DP. All three interventions arms will have either SP or DP placebo to ensure adequate blinding is achieved in the study. Follow-up for the pregnant women will end approximately 6 weeks after giving birth. In the second phase of the study, all children born to pregnant women enrolled in the study will be followed from birth until they reach 36 months of age. Children born to women randomized to receive 3 doses of SP during pregnancy will receive DP every 3 months between 2–24 months of age. Children born to women randomized to receive 3 doses of DP or monthly DP during pregnancy will receive either DP every 3 months or monthly DP between 2–24 months of age. To ensure adequate blinding, children who will receive DP every 3 months will be given DP placebo during the months they will not be taking DP. Children

will then be followed an additional year between 24–36 months of age following the interventions.

The details outlined in this statistical analyses plan will only focus on Phase I of the study involving pregnant women.

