Placental blood by LAMP	n/N (%)	n/N (%)			n/N (%)		
Maternal blood by microscopy	n/N (%)	n/N (%)			n/N (%)		
Maternal blood by LAMP	n/N (%)	n/N (%)			n/N (%)		
Cord blood by microscopy	n/N (%)	n/N (%)			n/N (%)		
Cord blood by LAMP	n/N (%)	n/N (%)			n/N (%)		
Birth outcomes							
Spontaneous abortion	n/N (%)	n/N (%)			n/N (%)		
Stillbirth ^b	n/N (%)	n/N (%)			n/N (%)		
Low birth weight ^b	n/N (%)	n/N (%)			n/N (%)		
Preterm delivery ^b	n/N (%)	n/N (%)			n/N (%)		
Congenital anomaly ^b	n/N (%)	n/N (%)			n/N (%)		
Composite adverse birth outcome	n/N (%)	n/N (%)			n/N (%)		

^a Reference group

^b Only includes those at least 28 weeks gestational age

Table 12. Longitudinal outcomes assessed during pregnancy

Outcome	Treatment arm						
	3 dose SP ^a		3 dose DP		Monthly DP		
Incidence measures	Events ^b	Events ^b	IRR (95% CI)	p-value	Events ^b	IRR (95% CI)	p-value
Symptomatic malaria	xx (x.xx)	xx (x.xx)			xx (x.xx)		
Prevalence measures	Prevalence	Prevalence	RR (95% CI)	p-value	Prevalence	RR (95% CI)	p-value
Detection of malaria parasites by LAMP							
All routine visits	n/N (%)	n/N (%)			n/N (%)		
20 weeks gestational age	n/N (%)	n/N (%)			n/N (%)		
24 weeks gestational age	n/N (%)	n/N (%)			n/N (%)		
28 weeks gestational age	n/N (%)	n/N (%)			n/N (%)		
32 weeks gestational age	n/N (%)	n/N (%)			n/N (%)		
36 weeks gestational age	n/N (%)	n/N (%)			n/N (%)		
40 weeks gestational age	n/N (%)	n/N (%)			n/N (%)		
Anemia defined as hemoglobin level < 11 g/dL							
All routine visits and delivery	n/N (%)	n/N (%)			n/N (%)		
20 weeks gestational age	n/N (%)	n/N (%)			n/N (%)		
28 weeks gestational age	n/N (%)	n/N (%)			n/N (%)		
36 weeks gestational age	n/N (%)	n/N (%)			n/N (%)		
At the time of delivery	n/N (%)	n/N (%)			n/N (%)		

^a Reference group

^b Number of events (incidence per person year at risk)

9 Safety and Tolerability Analyses

Safety and tolerability will be evaluated during the period following the 1st dose of study drug administration through the end of the observation period (6 weeks post-partum) or premature study withdrawal.

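### Table 10 classes every delivery before 28 weeks as a spontaneous abortion whatever the vital status, so a live birth before 28 weeks can never count as preterm or low birth weight

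*SAP*

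**What the plan says.** In Table 10 (SAP section 8.1) the numerator for spontaneous abortion is "Delivery at < 28 weeks gestational age", over all deliveries. Neither fetal death nor the manner of onset enters the definition.

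Stillbirth, LBW, preterm delivery and congenital malformation all use deliveries at 28 weeks or later as denominator. Preterm delivery has the numerator "Gestational age < 37 weeks", and its missing-data entry is "Withdrawn prior to delivery or < 28 weeks gestational age". The LBW entry is "Withdrawn prior to delivery or < 28 weeks gestational age or no birth weight". Vital status appears in one row only, stillbirth ("Infant born deceased"), and there only from 28 weeks. Table 11 (section 8.3) marks the same four outcomes with footnote b: "Only includes those at least 28 weeks gestational age". The abortion row of Table 11 carries no footnote.

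Section 3.2.2 lists the birth outcomes as "congenital malformations, preterm delivery, late spontaneous abortion, LBW (<2500g), stillbirth, or a composite of all of these". Section 3.3 names the same components for the composite. Neither section sets a lower gestational limit for preterm delivery or LBW. In Table 10 the composite includes spontaneous abortion and is taken over all deliveries.

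**The concern.** A 28-week boundary is a workable way to separate two kinds of fetal death, abortion and stillbirth. Table 10 applies it to live births as well. An infant born alive at 27 weeks and an infant born dead at 27 weeks get the same code, and the live one leaves the preterm and LBW analyses as if its data were missing. Its gestational age is known, and it lies below the 37-week threshold.

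Section 2.1 of the SAP names preterm delivery and LBW among the harms of malaria in pregnancy. The rule removes the most premature live births from both. Gestational age at delivery arises after randomisation, so the removal need not be balanced between arms. The same births would be added to the abortion row, and a reader of Table 11 would have no note saying that the row may contain live births.

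**Working it through.** The SAP states no figure on this point that could be reproduced. The check has two parts: running test deliveries through the Table 10 rules, and working out how far one affected birth moves the component rates.

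**1. Rules applied to test deliveries**

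Rules: abortion = gestational age below 28 weeks. If 28 weeks or more: stillbirth = born dead; LBW = below 2500 g; preterm = below 37 weeks. If below 28 weeks, these three are missing. Composite = any component present. Malformation is left out of the test cases.

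| Delivery | Abortion | Stillbirth | LBW | Preterm | Composite |
|---|---|---|---|---|---|
| 24 weeks, alive, 650 g | yes | missing | missing | missing | yes |
| 27 weeks, alive, 950 g | yes | missing | missing | missing | yes |
| 27 weeks, dead, 950 g | yes | missing | missing | missing | yes |
| 28 weeks, alive, 1100 g | no | no | yes | yes | yes |
| 39 weeks, alive, 3000 g | no | no | no | no | no |

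Rows 2 and 3 are coded identically although one infant is alive. Between rows 2 and 4 one week of gestation turns an abortion into a preterm LBW birth. The composite is yes in each of the first four rows, so it does not depend on how the early live births are labelled.

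**2. Size per affected birth**

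Inputs:
- n = 90 deliveries per arm. This is an assumption, in line with the 90 women per arm with placental outcomes in Table 4 of the SAP.
- x = 9 preterm deliveries at 28 weeks or later, about 10%. Also an assumption.
- k = live births before 28 weeks in the arm. The SAP gives no value, so k is varied from 0 to 3.

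Preterm rate under Table 10: x / (n − k). With early live births counted: (x + k) / n. The difference is (k / n) × (1 − p), where p = x / (n − k).

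| k | Table 10 | Early live births counted | Difference |
|---|---|---|---|
| 0 | 9/90 = 10.0% | 9/90 = 10.0% | 0 |
| 1 | 9/89 = 10.1% | 10/90 = 11.1% | 1.0 point |
| 2 | 9/88 = 10.2% | 11/90 = 12.2% | 2.0 points |
| 3 | 9/87 = 10.3% | 12/90 = 13.3% | 3.0 points |

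The result depends little on the assumed preterm rate. For k = 1, at about 5% it is 4/89 = 4.5% against 5/90 = 5.6%; at about 15% it is 13/89 = 14.6% against 14/90 = 15.6%. The formula also holds for LBW, with p the LBW proportion, if the infant is weighed. The abortion rate is too high by k/n, which is 1/90 = 1.1 points per birth.

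For the risk ratio, suppose the comparison arm has 9/90 and no early live birth. With k = 1 in the other arm, Table 10 gives (9/89)/(9/90) = 1.01, against (10/90)/(9/90) = 1.11 with the birth counted. With k = 3 the values are 1.03 and 1.33.

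**The case against.** The strongest reply is that the 28-week limit is explicit and prespecified, and that it is applied in the same way in the numerators, denominators and missing-data entries of Table 10 and again in Table 11. The outcomes are secondary, the composite captures every affected birth, and with no live birth before 28 weeks nothing changes. All of this stands. It limits the weight of the point but does not answer it: a rule can be consistent and still give a live birth the wrong label, and no other section of the SAP repairs this.

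Three stronger readings are tempting, and the SAP does not support them.

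- A reader might infer that Table 10 contradicts section 4.1, under which "all children born to pregnant women enrolled in the study will be followed from birth until they reach 36 months of age". It does not. That sentence says who is followed in the second phase; it does not define birth outcomes, and section 4.1 limits this SAP to the first phase. Following a child is compatible with any classification of the mother's delivery.
- A reader might infer that the component risk ratios in Table 11 are wrong as they stand, or that live births could make up half or more of an arm's abortions. The first is true only if such births occur. The second needs an expected number of abortions, which the SAP does not give.
- A reader might infer that the safety board would be misled at the interim look. Section 6.5.4 provides brief clinical descriptions of key events beside the counts by arm, so the board would not depend on the label alone.

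**Conclusion.** The point holds as a flaw of definition in secondary component outcomes. Any live birth before 28 weeks would be reported as an abortion and left out of preterm delivery and LBW. Each such birth raises the abortion rate by about 1.1 percentage points and lowers the preterm rate by about 1 point, and the LBW rate by a similar or smaller amount, assuming about 90 deliveries per arm. The number of such births is unknown and may be zero, in which case no result changes. The primary histopathology outcome, the sample size and the composite are untouched. It is still worth settling before unblinding, because otherwise the handling of one or two births may be decided with the arm known.

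**What to change.** In Table 10:

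- **Abortion:** restrict the row to pregnancy losses before 28 weeks without a live birth, whatever the onset. Requiring spontaneous onset would leave an early loss of another kind in no row, and it would drop out of the composite.
- **Preterm delivery and LBW:** count live births before 28 weeks as preterm, and as LBW if weighed below 2500 g. Add them to the denominators of these two rows and take the below-28-weeks entry for live births out of the missing-data column.
- **Congenital malformation:** include live births before 28 weeks when the infant was examined.
- **Stillbirth:** leave at 28 weeks or later.

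Split footnote b of Table 11 to match: the present restriction for stillbirth, the extended denominator for the other three. Keep the current 28-week definitions as a sensitivity analysis.

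**Cost:** wording in four rows and one footnote. The stillbirth row already needs vital status, and section 4.5 lists gestational age and birth weight among the delivery records. The SAP gives only the title of the child's delivery form, so the sponsor should confirm that vital status is recorded for deliveries before 28 weeks. The main rates become slightly less comparable with reports that use a fixed 28-week cut-off; the sensitivity analysis covers this. The new preterm and LBW denominators still exclude early fetal losses, which also arise after randomisation, so these two rows should be read beside the composite over all deliveries.

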3.3 Derived Variables

Composite adverse birth outcome will be a derived variable defined as the presence of any preterm delivery, congenital malformations, spontaneous abortion, low birth weight (<2500g), or stillbirth.

4 Study Methods

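### Table 10 does not carry the missing-data rules for low birth weight and malformation into the composite adverse birth outcome, so some incompletely assessed deliveries count as non-events

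*SAP*

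**What the plan says.** SAP section 8.1 makes Table 10 the governing source: "Definitions and criteria used to generate estimates of all primary and secondary efficacy outcomes are presented in Table 10 below". Three of its rows matter here.

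- **Low birth weight.** Missing if "Withdrawn prior to delivery or < 28 weeks gestational age or no birth weight". The imputation column offers one rescue: "Inferred if no birth weight but weight available with 7 days of birth".
- **Congenital malformation.** Missing if "Withdrawn prior to delivery or < 28 weeks gestational age or infant unavailable for examination". Nothing is imputed.
- **Composite adverse birth outcome.** The numerator is "Any of the following: spontaneous abortion, stillbirth, low birth weight, preterm delivery, or congenital malformation" and the denominator "All deliveries". The only missing-data reason is "Withdrawn prior to delivery", and nothing is imputed.

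Section 3.3 adds no rule for unknown components: "Composite adverse birth outcome will be a derived variable defined as the presence of any preterm delivery, congenital malformations, spontaneous abortion", followed by the remaining components. Section 8.1 also says that for twins an outcome counts if either child has it. It does not say what happens when one child is unaffected and the other unknown.

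**The concern.** The SAP expects some births without a weight and some infants without an examination, since it writes missing-data categories for both. The documentation list under Table 2 (section 4.5) records length of admission only for hospital deliveries, so births elsewhere are also foreseen. Such a delivery is missing for the component concerned. In the composite it stays in the denominator and, if nothing else was observed, cannot enter the numerator. Unknown is then coded as unaffected.

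Two things are at stake. The composite prevalence is pulled down in every arm. If the share of unassessed deliveries differs by arm, the risk ratio in Table 11 moves as well. Two analysts could also take different denominators from the same data, because the SAP does not say when a partly observed composite is evaluable.

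**Working it through.** The SAP states no rate, sample size or power for the composite, so there is no figure of its own to reproduce. The check sets the rows side by side and then sizes the effect on stated assumptions.

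**Which deliveries are affected.** For spontaneous abortion, stillbirth and preterm delivery, Table 10 lists no missing-data reason beyond withdrawal or, for the last two, delivery before 28 weeks. A delivery before 28 weeks is itself an event through the abortion component. A stillborn or preterm infant with no recorded weight still counts as an event. Only deliveries at 28 weeks or later with no observed event and an unknown weight or examination are misclassified.

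**Inputs (all assumptions, none from the SAP).**
- a = risk through the always-observed components (abortion, stillbirth, preterm): 8–12%
- b = risk through low birth weight or malformation only, among the rest: 5–10%
- m = share with weight or malformation status unknown, unrelated to outcome: 2–10%
- deliveries per arm: 90. Section 5 gives 90 women per arm with placental outcomes; using it here is an assumption.

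**Formulas.**
- True risk = a + (1 − a)b
- Risk under the literal rule = a + (1 − a)b(1 − m)
- Risk if only indeterminate deliveries are dropped = [a + (1 − a)b(1 − m)] / [a + (1 − a)(1 − m)]
- Indeterminate deliveries per arm = 90(1 − a)m

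**Understatement of risk.**
- Largest (a = 8%, b = 10%, m = 10%): true 0.08 + 0.92 × 0.10 = 17.2%; literal 0.08 + 0.92 × 0.10 × 0.90 = 16.3%; relative change −5.3%.
- Smallest (a = 12%, b = 5%, m = 2%): true 0.12 + 0.88 × 0.05 = 16.4%; literal 0.12 + 0.88 × 0.05 × 0.98 = 16.3%; relative change −0.5%.
- Indeterminate deliveries: from 90 × 0.88 × 0.02 = 1.6 to 90 × 0.92 × 0.10 = 8.3 per arm.

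**Distortion of a null risk ratio, 2% against 10% unassessed.**

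| a | b | literal risk, m = 2% | literal risk, m = 10% | apparent RR |
|---|---|---|---|---|
| 8% | 5% | 12.51% | 12.14% | 0.971 |
| 8% | 10% | 17.02% | 16.28% | 0.957 |
| 12% | 5% | 16.31% | 15.96% | 0.978 |
| 12% | 10% | 20.62% | 19.92% | 0.966 |

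The range is about 0.96–0.98, or the reciprocal (about 1.02–1.05) if the arms are swapped.

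**Why dropping only the indeterminate deliveries is not neutral.** Incompletely assessed deliveries with a known event stay in, while those without one leave. At a = 8%, b = 10%, m = 10% the result is 0.1628 / 0.908 = 17.9%, against a true 17.2%. With 2% against 10% unassessed, a null RR becomes about 1.03–1.05 over the same grid, for example 17.93/17.34 = 1.03.

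**How far the unstated rule can move one arm (hypothetical counts).** With 90 deliveries, 14 known events and 5 indeterminate:
- counted as no event: 14/90 = 15.6%
- dropped: 14/85 = 16.5%
- counted as events: 19/90 = 21.1%

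**The case against.** The strongest reply is that the SAP never says these deliveries are unaffected. Sections 6.2 and 8.3 restrict analyses to women with evaluable data, or with data on the outcome, and section 6.4 sets aside women who cannot supply data for an outcome. An analyst could exclude indeterminate deliveries on that basis. This does not settle the matter. Section 6.4 is worded for the primary analysis, none of these sections says when a partly observed composite is evaluable, and excluding such deliveries would conflict with the denominator in the composite row.

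The design also limits exposure. A planned hospital delivery is an inclusion criterion (section 4.3.1), birth weight is part of delivery documentation (section 4.5), and a weight within 7 days rescues some low birth weight data. Double blinding makes missingness that differs by arm less likely. Table 11 shows n/N for each component, so gaps would be visible. All of this stands, and it keeps the point minor.

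Two stronger readings are tempting, and the SAP supports neither.

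- A reader might infer that the component and composite rows contradict each other. They are different outcomes, and a denominator of all deliveries is natural for a composite that includes spontaneous abortion. The defect is that the component rules are not carried through.
- A reader might scale the whole composite by the unassessed share. With a 20% risk, 0.20 × 0.90 = 18.0% against 0.20 × 0.98 = 19.6% gives an RR of 0.92. That assumes abortions, stillbirths and preterm deliveries also vanish when a weight or examination is missing. Table 10 still counts them.

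**Conclusion.** The point holds as a small misclassification. Taken literally, the composite row codes a delivery at 28 weeks or later with no observed event and an unknown weight or examination as having no adverse outcome. Under the assumed inputs, risk is understated by about 0.5–5% in relative terms. A null RR shifts to about 0.96–0.98 only if unassessed deliveries differ by arm as much as 2% against 10%; with equal missingness and equal risks the RR is unaffected. The sizes rest on assumed rates and on missingness unrelated to outcome within arm. The primary endpoint, sample size and interim safety boundaries are not touched.

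**What to change.** Amend the composite row of Table 10, before unblinding for the final analysis, as follows.

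1. Class a delivery at 28 weeks or later with no observed component event and an unknown birth weight or infant examination as indeterminate, not as a non-event.
2. State that a birth weight inferred from a weight within 7 days counts towards the composite, and how twins are classified when one child is unaffected and the other unknown.
3. For the estimate, multiply impute the unknown component, or analyse only fully assessed deliveries. Do not drop the indeterminate deliveries alone. If the second option is taken, define fully assessed for deliveries before 28 weeks. They are events by definition, and keeping all of them while removing incomplete later deliveries leaves a slight upward bias, so imputation is the cleaner choice.
4. Report the number indeterminate by arm, and show the versions with indeterminate counted as no event (the present all-deliveries rule) and as event, as bounds.

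The cost is a changed table row, a few sentences, a little more analysis work and a slightly less precise composite estimate.
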